## **1. PURPOSE OF THE STUDY AND BACKGROUND**

### **1.1. Purpose of the study**

This research is a traditional feasibility study designed to clinically characterize PreTel's uterine EMG/ECG fetal monitor for regional contraction detection and synchronization in laboring and non-laboring patients.

### **1.2. Background**

#### **Fetal monitoring**

Fetal monitoring is the primary method used by obstetricians for moment-to-moment assessment of the health of the fetus. Fetal heart rate and uterine contractions together comprise the two elements of a fetal monitor. Fetal monitors are used in 90% of all deliveries in the United States during labor [1]. Even in the outpatient setting, fetal monitoring is used to assess fetal well-being in pregnancies with common conditions, such as obesity [2]. Fetal monitoring tests are, thus, routinely performed in the outpatient and inpatient settings.

#### **Maternal Heart Rate monitoring**

Maternal heart rate data are sometimes confused with fetal heart rate data, and it is clinically useful to independently measure the maternal heart rate. If different rates are obtained, it is clear that the fetal heart rate reported by the monitor does indeed come from the fetus. Legacy recording of the maternal heart rate occurs through use of a pulse oximeter placed on the maternal finger.

#### **Legacy fetal monitoring - Non-invasive method**

Uterine contractions can be measured using a plunger-type mechanical device (called the Tocodynamometer, or "Toco"), and the fetal heart rate can be measured using an electronic stethoscope device (called the Doppler). To obtain tracings, each device is held firmly against the maternal abdomen by straps, which causes discomfort to the patient after several hours. To maintain accurate recordings each device must be correctly aligned, and the alignment needs frequent adjustment by nursing staff. Patient movements, including ambulation, can displace the sensors, so patients are commonly asked to lie still in bed.

Accurate monitoring while ambulating is difficult or impossible. Even with patients lying still and with dedicated nursing attention, this technology is ineffective on average 15% of the time, with even poorer performance in obese patients [3].

#### **Legacy fetal monitoring - Invasive fetal monitoring.**

Because ongoing assessment of the fetus is critically important, invasive monitoring is often performed when non-invasive legacy methods fail. Here, a fetal scalp electrode (FSE) is used to measure the fetal heart rate, and an intrauterine pressure catheter (IUPC) is used to measure uterine contractions.

For the FSE, a silver wire is attached to the fetal scalp. This provides direct electrical contact with the fetus and allows recording of a reliable ECG signal for heart rate determination. The IUPC is a tube that is inserted through the vagina and cervix, and into the uterine cavity. The IUPC reports the pressure generated inside the uterus, which is a direct measure of the contraction forces produced. The use of these internal direct measurements is considered the gold standard for fetal monitoring.

Use of invasive monitoring requires that the amniotic membranes be ruptured (either naturally or intentionally). Thus, there are potential complications that arise in the setting of IUPC/FSE monitoring, most commonly maternal fever [4], which is suggestive of intrauterine infection.

### **The need for a more reliable non-invasive fetal monitor**

If a more reliable non-invasive fetal monitor was available, it would reduce the need to use invasive (IUPC/FSE) methods, and thereby reduce the risks to mother and baby.

Additionally, a reliable non-invasive fetal monitor not requiring straps would allow for improved patient comfort and for patient and care provider desired maternal ambulation.

### **An alternative to the legacy non-invasive fetal monitor (Toco/Doppler)**

Most are familiar with electrocardiography (ECG, or EKG in German), where electrical impulses causing contractions of the heart are assessed using sensor pads on the chest. The pads “sense” the signals created by the heart, and do not create or store any electricity. The uterus is a muscle emitting electrical signals when it contracts. Uterine signals (here called EMG, for electromyography) can be separated from heart signals because the uterus and heart create signals at different frequencies. Thus, both heart and uterine signals appear in each sensor and then the signals can subsequently be amplified and separated by filtering. Like the Toco and Doppler, EMG and ECG are non-invasive. Non-invasive methods by definition do not pose a risk to the patient.

Hence, as an alternative to the plunger-based Toco, it is possible to use EMG to measure the bioelectrical signals that originate from the uterus, and then convert these signals to into tracings that mimic the Toco tracing [5]. Similarly, it is possible to measure the ECG of the fetal heart, then convert these signals to a fetal heart rate tracing. In this manner, an EMG/ECG –based fetal monitor can be constructed. Additionally, the EMG/ECG monitor can detect the maternal ECG, and hence the maternal heart rate can be determined. This could then replace the additional finger pulse oximeter, reducing the number of lines attached to the patient.

The clinical impetus to convert to an EMG/ECG fetal monitor is that it would overcome many of the limitations of the Toco/Doppler [6]. Specifically, an EMG/ECG monitor should be more reliable, require less nursing intervention, be more comfortable to patients, and more easily allow ambulation.

### **First generation EMG/ECG fetal monitors**

Because of these potential benefits, fetal monitors using EMG/ECG technology (including display of maternal heart rate) have been developed. These first-generation devices use traditional, circular ECG pads to record fetal ECG, maternal ECG, and uterine signals. However, ECG pads were specifically designed to record heart signals, and yield only small signals from the uterus. Small signals require a moderate amount of data processing suggesting sub-optimal reliability. Reporting of false positive contractions is a problem with EMG reliability that is not seen with legacy methods, and this creates a problem that clinicians have no experience in accommodating.

### **PreTel's next generation regional contraction uterine EMG (uEMG)/ECG fetal monitor**

The next generation EMG/ECG fetal monitor will need to overcome the limitations of the first-generation monitors. Furthermore, PreTel's regional contraction uEMG/ECG monitor provides information that previously was unavailable with any non-invasive technology. Three components of PreTel's monitor exhibit advantages over the first generation. They are (1) the sensors, (2) the amplifier, and (3) the method of data analysis.

#### **Area uEMG sensors**

In our research, we discovered that ECG-type pads are poorly suited to record uterine signals because of major differences of physiology between the organs [7]. In brief, heart signals travel parallel with the skin, while uterine signals arise from below. This phenomenon results in circular pads detecting only very small signals that are difficult to separate from background noise. To more efficiently measure the rising uterine signals, we developed a directional sensor, (which we call “area sensor”). These were evaluated at URMC under RSRB#59426 in 2016-2017. These uEMG sensors are made from the same material as standard ECG pads, but differ only in shape – an open hexagon, measuring 6 cm x 6 cm, (i.e. the hexagon surrounds an open “area”). The unique shape confers directionality to the sensor, efficiently sensing signals that arise from below. This gives our sensors the ability for typical signal detection of 1500  $\mu$ V, which is 5 times greater voltage than the largest voltage reported using pad-type sensors. Furthermore, our sensors provide for, the first time, spatial resolution to identify local uterine contractile activity.

Not surprisingly, both the fetal and maternal ECG is also observable using our area sensors.

Further study is required to convert and display these signals into clinically useful fetal and maternal heart rates.

Though this study, we anticipate that by measuring the extent of synchronization of several regions on the uterus, we will be able to determine which contractions represent true labor, and which represent false labor. First generation EMG analysis measures the relative power of the signals coming from the uterus. Our method analyzes the timing of events from the many sensors/regions that sample a large surface of the uterus, a procedure called “event analysis”. Furthermore, we hypothesize that a transition from unsynchronized regional contractions to fully synchronized contractions will represent the onset of true labor.

## **2. STUDY DESIGN**

### **2.1. Overview**

This is an NIH SBIR feasibility and efficacy study. This study seeks to validate the reliability of the PreTel Regional Contraction uEMG/ECG Fetal Monitor in accurately determining contraction and the fetal heart rate. The study also seeks to validate the reliability with which the monitor is able to determine true labor contractions from false labor contractions. The study will achieve these goals by utilizing the PreTel Regional Contraction uEMG/ECG Fetal Monitor concurrently with standard fetal and uterine monitoring prior to and during labor.

Patients will be approached as they present for evaluation of labor in Triage and Labor and Delivery. After obtaining consent, we will have the subject sit, slightly reclining. We will place up to 15 EMG electrode pads over her abdomen, spanning most of the surface of the uterus, plus one ground electrode. The arrangement of the electrodes will be documented. If the patient consents to photo-documentation of the arrangement, then a de-identified photo of the sensor arrangement will be taken and stored electronically. The purpose of the image is to assess the

overall abdominal coverage of all EMG/ECG sensors and the placement of the legacy (traditional) monitors. The photograph may be taken before, during or after the completion of testing, so long as it accurately represents the locations of the area and pad sensors of the study device, and the Toco and Doppler of the legacy devices. Should significant adjustments of the study or legacy recording devices occur, such that the locations change, additional photographs may be taken to provide additional information of sensor locations at different times during testing. If the subject requests that a photograph not be taken, or if there is a technical reason that a photograph cannot be obtained, no photograph will be taken, and the subject will continue as a research subject (i.e. She will not be withdrawn from the study.) Failure to obtain an image will not be considered a breach of protocol and will not be reportable as such.

We will record multichannel EMG signals for 60 minutes for each subject. The subject will be eligible for compensation as outlined in section 10.1.

All health care management decision will be based on the standard obstetrical testing.

At the conclusion of the recording, the pads will be removed from the subject. Pads will also be removed at patient request at any time during the study procedure.

We will examine the subjects' medical record for the following PHI, which will be recorded in the Case Report form (CRF):

1. Documentation of key elements of the consent process
2. Date and time of study
3. Patient BMI (weight and height)
4. Patient age, race/ethnicity
5. Due date
6. Cervical dilation prior to start of study, any cervical dilation measurements recorded for clinical purposes during study (noting times)
7. Copy of the legacy (standard) fetal monitor strips obtained during study
8. Placement and location of the sensors on the subject (Photo, if patient consents to photo)
9. If labor was spontaneous or induced/augmented
10. Mode of delivery (vaginal vs Cesarean section) and delivery time and date.
11. Any medications administered before or during EMG recordings, such as Pitocin, nifedipine, magnesium sulfate, terbutaline, etc.

Should data be missing, a decision regarding the applicability of the recording will be made on a case-by-case basis by the sponsor.

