### 3. CHARACTERISTICS OF THE RESEARCH POPULATION

#### 3.1. Subject Characteristics

##### a) Number of Subjects:

We plan to recruit up to 50 study subjects to complete the entire 60 minutes of testing and consent to have their chart reviewed after delivery to collect all objective outcome data as outlined in our study plan. Data from those who start the uEMG recordings but are unable to complete the full duration will still be analyzed so long as the reason for their withdrawal is not secondary to their withdrawal of consent. Those who withdraw consent will be excluded for data collection and analysis.

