Study personnel will also record the participants name and Medical Record Number in an I-Drive password protected database in order to select a unique identifier code, which will be used to label all EMG data and record the study data points as outlined above. Each subject will be coded per the following: mm/dd/yy-xx, where mm/dd/yy is the date of study, and xx refers to subject #01 through 50. All data sets, including the EMG tracings, fetal ECG tracing, and the CRF will be coded by the number.

Recording of the MRN and name is necessary in order to facilitate accessing the subjects' delivery records after completion of the study. Electronic accessibility to this key is necessary so that study investigators can enroll patients in triage, L&D and the birth center as well as at the out-patient URMC-affiliated obstetric offices, which are not in close proximity to the locked office of the PI.

All collected data will be recorded on Case Report Forms (CRF), attached in appendix 2. These will be copied and sent to [name] (recipient of NIH SBIR grant). A copy will be saved at URMC in the locked office of the local PI [name].

At the completion of the study all patient-identifying information will be kept in a secure locked filing cabinet. The time line for destruction will be no less than 10 years following study completion based on institutional protocol.

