For both the preterm or term subjects who present to triage, there is the possibility that they may not ultimately progress in labor. These subjects are also eligible for an EMG study session for 60 minutes while their labor status is being evaluated. If they are deemed to not be in labor (i.e. no cervical change) and are discharged (or admitted for extended monitoring, as may occur in the preterm setting or at term for “therapeutic rest”), they will not be excluded from analysis, and they will be allowed to participate in another session either when they begin laboring (i.e. if admitted) or if they are discharged and then return to Triage for another labor evaluation. Recordings may be stopped and restarted multiple times for a single subject if needed.

During the 60+ minutes of EMG pad placement, subjects must also have standard tocometry monitoring and fetal heart rate monitoring. The standard monitoring can consist of either external tocodynamometry (Toco) or an intra-uterine pressure catheter (IUPC) and either external Doppler monitoring of the fetal heart rate or a fetal scalp electrode (FSE). Which type of monitoring is used will be at the discretion of her regular obstetric care team and will not be altered by participating in the study (i.e., the study will not require the patient to have internal monitoring IUPC/FSE). Participation during the 60 minutes of recording does however require some form of continuous monitoring, and therefore subjects desiring intermittent fetal heart rate auscultation or intermittent palpation for contractions, will not be eligible for participation unless they are willing to have standard monitoring for the duration of the study period. Clinical decisions will only be made based on standard uterine and fetal monitoring and examinations.

Uterine EMG recordings, along with the fetal monitoring paper record, will be sent to PreTel. Assessment of the recordings for uterine contractility and fetal heart rate will then be performed by those investigators trained in the analysis ([name]). The EMG data will be compared to the tocometry data to determine correlation or “R” value.

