### **5.2. Costs to the Subject**

There will be no cost to the patient or the patient's insurance as a result of study enrollment. The electrodes, EMG, and computer are being provided by the study Sponsor.

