## 12. CONFIDENTIALITY OF DATA AND INFORMATION STORAGE

Participants’ consent forms will be kept in a secure locked filing cabinet in [name]’s locked office.

Patients’ names and medical record numbers will be linked to a code by date as follows: mm/dd/yy-xx, where mm/dd/yy is the date of study, and xx refers to subject #01 through 50. A master key will be maintained on a password-protected spreadsheet on the secure OB/GYN I-Drive at URMC.

The CRF's will be kept in a locked file in the office of [name].

Uterine EMG recordings will be labeled with the participants' unique identifier codes and not with their names, MRNs or birthdates.

Access to the I-Drive Key will be available only to those personnel responsible for consenting participants. Once all data is collected and EMG recordings have been completed this EMG data will be sent to the PreTel, Inc. electronically via e-mail, as there is no identifying patient information recorded on these. The data sheet is also de-identified, with only the unique identifier listed; this data sheet will also be sent to PreTel, Inc., (a.k.a. [name]) via URMC email. The Key spreadsheet will remain at URMC in the password protected file on the encrypted I-Drive. Following completed enrollment the password to the Key sheet will be changed so that only the PI's have access to this key and study coordinators will no longer have access.

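### The sponsor decides case by case whether a recording with missing data counts, with no criteria, time point or blinding, although it also receives the device data and the delivery outcome

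*Combined protocol and SAP*

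**What the plan says.** Section 2.1 lists eleven items to be taken from the medical record onto the case report form (CRF). Directly after the list comes the rule: "Should data be missing, a decision regarding the applicability of the recording will be made on a case-by-case basis by the sponsor". The only gap with a rule of its own is the sensor photograph, whose absence neither removes the woman from the study nor counts as a protocol breach.

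On what the sponsor receives:
- Section 5: "Uterine EMG recordings, along with the fetal monitoring paper record, will be sent to PreTel".
- Section 2.1, item 10 of the CRF list: "Mode of delivery (vaginal vs Cesarean section) and delivery time and date". Section 4.1 has CRF copies going to the holder of the NIH grant.
- Section 12, on the de-identified data sheet: "this data sheet will also be sent to PreTel, Inc".
- Section 12, on timing: "Once all data is collected and EMG recordings have been completed this EMG data will be sent to the PreTel, Inc. electronically via e-mail".

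Sections 5 and 11.2 place the analysis with PreTel, the study sponsor. Section 14.2 (Contraction analysis) classifies labor status by time to delivery: within 24 hours, 24 to 72 hours, or 72 hours and more.

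On recordings cut short, section 3.1 a) says: "Data from those who start the uEMG recordings but are unable to complete the full duration will still be analyzed", except where consent is withdrawn. Section 14.1 sets recruitment at up to 50 to make up for women who are enrolled and then left out because they could not finish the session.

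**The concern.** Whether a recording belongs in the analysis should not depend on whether the device did well on it. Here the discretion sits with the party that makes the device, analyses its signal and can see the outcome against which it is judged. Section 2.1 sets out to validate the monitor's reliability, including its separation of true from false labor. An exclusion made with the prediction and the delivery time both in view can improve the apparent result, and the plan requires no log from which a reader could detect it. Recruiting up to 50 for a required 23 means that exclusions need not show up as a shortfall either. The opposing statements on unfinished recordings add a second open choice about the analysis set.

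**Working it through.** **1. Who decides, and with what in hand.** The decision is the sponsor's (2.1). EMG and legacy strip go to PreTel (5). The CRF list includes delivery time and date (2.1, item 10), and a CRF copy or data sheet leaves the site (4.1, 12). That PreTel is the sponsor is inferred, since the title page is not in the text reviewed. Section 5.2 says "The electrodes, EMG, and computer are being provided by the study Sponsor", section 9.1 places the equipment supplier at PreTel, and sections 11.2 and 12 send the de-identified data to the sponsor and to PreTel respectively.

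**2. When.** Section 2.1 is silent. Section 12 sends the EMG after data collection. If that includes the delivery items, the outcome can be known when the EMG arrives. Section 14.2 orders prediction before correlation but gives no lock or blinding and does not mention exclusions.

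**3. What counts as missing.** The sentence follows the CRF list, so its natural scope is those items. Lost EMG or ECG signal is not on the list. Endpoints 1.1, 2.1 and 2.3 already treat interpretability as the quantity measured.

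**4. Incomplete recordings.** Section 3.1 a) analyses them; section 14.1 describes such women as excluded. Both cannot stand.

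**5. Size, as an illustration.** Section 14.1 gives N = 23, a 50% minimum, expected ratios of .75/.25, alpha 0.05 and beta 0.8. It names odds-ratio statistics but no formula or sidedness. Reading beta = 0.8 as power 0.80, a one-sided one-sample test of a proportion reproduces 23:

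n = [1.645·√(0.5·0.5) + 0.842·√(0.75·0.25)]² / (0.75 − 0.50)² = 22.5, rounded up to 23.

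The exact rule of at least 16 correct of 23 has alpha 0.0466 and power 0.804.

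Suppose 15 of 23 women are classified correctly and 3 of the 8 incorrect recordings are dropped:
- before: 15/23 = 65.2%, exact one-sided p against 50% = 0.105
- after: 15/(23 − 3) = 15/20 = 75.0%, p = 0.021

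This needs at least 3 of the 8 incorrect recordings to have a missing item. If items are missing at rate q independently of correctness, that chance is P(Bin(8, q) ≥ 3): 3.8% at q = 10%, 20.3% at 20%, 44.8% at 30%.

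The next table gives the false-positive rate when true accuracy is 50% and any misclassified recording with a missing item may be dropped. No rate q is in the documents, so a range is shown.

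| q | N = 23 | N = 50 |
|---|---|---|
| 0 | 0.0466 | 0.0325 |
| 5% | 0.0500 | 0.0527 |
| 10% | 0.0585 | 0.0740 |
| 20% | 0.0887 | 0.1466 |
| 30% | 0.1408 | 0.2633 |

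The effect is small when few recordings have gaps and material when many do.

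**The case against.** The strongest case against runs as follows.

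- **Scope.** The sentence concerns CRF items, not lost signal, and the interpretability endpoints already count signal loss. This stands: a reader might infer that recordings with lifted pads or lost signal can be discarded, but the text does not clearly say so.
- **Missing references.** If the delivery date is missing, the sponsor cannot know whether the labor prediction was right; if the strip is missing, agreement cannot be computed. This also stands. The discretion that matters is over other items, such as BMI, due date, medications and dilation. Nothing in the documents shows that those gaps go with poor device performance.
- **Safeguards.** Section 5 has the local investigator attest that each CRF is complete, and section 14.2 puts prediction first. Both help, but neither says who may exclude a recording, when, or on what knowledge.
- **Size.** The 15/23 example is constructed. Section 14.2 states no per-woman success threshold, and section 14.1 also counts 230 contractions. This stands, so the figures are illustrations only.
- **Feasibility of a lock.** Under endpoint 1.4 the cut-offs for the synchronization factor (SF) are to be learned from these data, so predictions cannot simply be frozen before outcomes are seen. This stands and shapes the fix.
- **It is a pilot.** Sections 1.1 and 14.1 say so in substance, but section 2.1 also claims efficacy and validation. A pilot still needs a defined analysis set.

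**Conclusion.** The concern holds in this form: the plan gives the sponsor open discretion over recordings with missing data, and nothing prevents its use after the device result and labor outcome are known. Sections 3.1 a) and 14.1 also conflict on incomplete recordings.

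A reader might go further and infer that unfavourable recordings will be removed, that every device metric would rise, or that a shift of about ten points is to be expected. The documents support none of these. They show no intent, state no missing-data rate, and give no basis for a uniform effect (on RMS error, for example). Nor is section 3.1 a) clearly contradicted by the missing-data sentence, since one concerns short recordings and the other missing items; the contradiction is with section 14.1.

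The conclusion rests on PreTel being the sponsor and on the CRF copy or data sheet carrying delivery time. The form itself, Appendix 2, is not in the text reviewed. It does not depend on the sample size calculation.

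**What to change.** Replace the missing-data sentence in section 2.1 with a fixed rule:

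- Every started recording without consent withdrawal is analysed for each endpoint whose reference data exist: the legacy trace for contraction and fetal heart rate endpoints, the delivery date for labor status.
- A gap in any other CRF item, such as BMI, due date or medications, does not exclude a recording.
- Lost EMG or ECG signal stays in the denominator as uninterpretable, as endpoints 1.1, 2.1 and 2.3 already imply.
- URMC staff apply and log the rule without seeing the EMG result and before delivery outcomes are linked to EMG results. They need to know only whether the reference exists. SF cut-offs need not be locked; they can still be derived from the data once the analysis set is settled.
- The number of exclusions and the reason for each are reported.

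Amend section 3.1 a) or section 14.1 so that they agree on recordings cut short.

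The cost is protocol wording, a small log at the site and a short delay in linking outcomes. Reported performance may be slightly less favourable. No visit, procedure or recruitment number changes.
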